3.6.2 Cumulative dose

Cumulative dose for any component of study treatment is defined as the total dose of the medication given during the study treatment exposure.

Cumulative dose will be summarized using descriptive statistics by treatment arm for each component of study treatment. For patients who do not receive any drug the cumulative dose will be set to zero.

The cumulative dose is defined according to the type of dosing schedule and is calculated from the DAR eCRF. It is expressed in mg for alpelisib/placebo and fulvestrant.

Alpelisib/placebo

Cumulative dose (mg) = Sum of doses of the study drug administered to the patient from the start date to the last date of study drug.

Fulvestrant

The cumulative dose for fulvestrant with cyclic administration should be defined based on the days when the subject is assumed to have taken a non-zero dose during dosing periods.

3.6.3 Dose intensity and relative dose intensity

Dose intensity (DI) for patients with non-zero duration of exposure is defined as follows.

DI (dosing unit / unit of time) = Cumulative dose (dosing unit) / Duration of exposure (unit of time).

For patients who did not take any drug the DI is equal to zero. Planned dose intensity (PDI) is the assigned dose by unit of time planned to be given to patients as per protocol in the same

dose unit and unit of time as that of the Dose Intensity. DI, PDI and Relative dose intensity (RDI) is defined as:

For alpelisib/placebo:

- DI (mg/day) = Cumulative dose (mg) / duration of exposure (days)
- PDI is 300 mg/day
- RDI (%) = DI (mg/day) / PDI (mg/day) *100

For fulvestrant:

- DI (mg/day) = Cumulative dose (mg) / duration of exposure (days)

Categorical summaries of alpelisib RDI and the continuous summaries of RDI (i.e. mean, standard deviation etc.) will be presented.

3.6.4 Dose reduction, interruption and permanent discontinuation

The number (%) of patients with dose reductions or interruptions and permanent discontinuations, and associated reasons, will be summarized separately for each study drug (alpelisib/placebo and fulvestrant). In addition, reasons for permanent discontinuation from the study drug will be summarized for both alpelisib/placebo and fulvestrant.

Dose administered (mg) and dosing frequency from the DAR eCRF will be used to determine the dose reductions and interruptions.

‘Dose permanently discontinued’ ticked box from the DAR eCRF will be used to determine permanent discontinuation.

Dose interruption

For alpelisib/placebo, an interruption is defined as a zero dose on one or more days between two non-zero doses.

Any two or more consecutive zero doses of alpelisib (e.g. in the sequence 300 mg daily, 0 mg, 0 mg, 300 mg daily) or fulvestrant will be counted as 1 interruption if the reasons for these two consecutive dose interruption are the same. It will be counted as two different interruptions only if the reasons are different.

For fulvestrant, an interruption is defined as a zero dose on one or more days between two non-zero doses.

For example, a 500mg dose on C1D1, a zero dose on C1D15 and a 500mg dose on C2D1 will constitute a single interruption.

The number (%) of dose interruptions along with reasons will be summarized.

Note: The last zero dose of alpelisib/placebo or fulvestrant is not considered as a dose interruption.

Dose reduction

For alpelisib/placebo, a dose reduction is defined as a decrease in dose from the protocol planned starting dose (e.g. from 300 mg daily to 250 mg daily) even if the dose decrease has been directly preceded by an interruption. On the other hand, if the dose decrease is followed by an interruption, with the dose resuming at the same level prior to the interruption (e.g. in the sequence 300 mg daily – 0 mg - 300 mg daily), the second dose decrease or change in dosing frequency will not be counted as dose reduction.

If, due to a dosing error, a patient receives a higher than planned starting dose and moves down to the planned starting dose then this is not considered a dose reduction. However if the dose change is from a higher than planned starting dose down to a lower than protocol planned starting dose, then this is considered a dose reduction (e.g. in the sequence: 350 mg daily, 300 mg daily, 250 mg daily; 250 mg is considered a dose reduction).

If, due to a dosing error, a patient receives a lower than previous non-zero dose and resumes later at the protocol specified dose reduction, then the lower dose received due to dosing error and protocol specified dose reduction are dose reductions (e.g. in the sequence 300 mg daily – 200 mg daily - 250 mg daily, then 200 mg and 250 mg are considered dose reductions).

If, due to a dosing error, a patient receives a lower than previous non-zero dose and resumes later at a lower than previous non-zero dose, then 2 dose reductions will be counted (e.g. in the sequence 300 mg daily - 250 mg daily – 200 mg daily, 250 mg and 200 mg are dose reductions).

Table 3-1 Examples of Dose Reduction for alpelisib

Sequence	Reduction
With dose change	
300 mg daily - 250 mg daily – 0 mg - 250 mg daily	1 reduction (the 1 st 250 mg)
300 mg daily – 300 mg daily – 0 mg - 250 mg daily	1 reduction (250 mg)
300 mg daily – 0 mg – 250 mg daily	1 reduction (250 mg)
With interruption	
300 mg daily – 0 mg - 300 mg daily	0 reductions
With dosing error	
300 mg daily – 250 mg daily – 200 mg daily*	2 reductions (250 mg, 200 mg)
300 mg daily – 200 mg daily* - 300 mg daily	1 reduction (200 mg)
300 mg daily – 200 mg daily* - 250 mg daily	2 reductions (200 mg, 250 mg)
300 mg daily – 400 mg daily* - 350 mg daily*	0 reductions since 400 mg and 350 mg are dose escalations not reduction
300 mg daily – 150 mg daily* - 300 mg daily	1 reduction (150 mg)
With dosing error at the 1st administration	
150 mg daily* - 300 mg daily	1 reduction (150 mg)

Sequence	Reduction
150 mg daily* - 0 mg - 150 mg*- 300 mg daily	1 reduction (150 mg)
150 mg daily* - 300 mg daily - 0 mg - 250 mg daily	2 reductions (150 mg and 250 mg)

*dosing error

There is no planned dose reduction for fulvestrant; in addition the reason for fulvestrant dose reduction is not collected in the eCRF. No analysis for fulvestrant will be done on the number of, and reasons for, reductions.

3.7 Concomitant therapy

Concomitant therapy is defined as all interventions (therapeutic treatments and procedures) besides the study treatment that were administered to a patient, coinciding with the study assessment period.

Concomitant therapy include medications (other than study drugs) starting on or after the start date of study treatment or medications starting prior to the start date of study treatment and continuing after the start date of study treatment.

Concomitant medications will be coded using the World Health Organization (WHO) Drug Reference Listing (DRL) dictionary that employs the WHO Anatomical Therapeutic Chemical (ATC) classification system and summarized by lowest ATC class and preferred term using frequency counts and percentages. Surgical and medical procedures will be coded using MedDRA and summarized by SOC and preferred term.

Concomitant medications, concomitant medications with specific impact on the analysis (See [Section 3.7.1](#)), procedures and significant non-drug therapies taken concurrently with study treatment will be listed and summarized by ATC class/SOC using frequency counts and percentages. Any prior medications, procedures or significant non-drug therapies starting and ending prior to the start date of study treatment will be listed. Analysis will be based on Safety set.

3.7.1 Concomitant medications with specific impact on the analysis

According to study protocol Table 14-1, the following medications are either prohibited during the treatment period in this study, or to be used with caution:

- CYP3A4, CYP2C8, CYP2C9 or CYP2C19 substrates
- Medications with a known risk of QT prolongation
- QT prolonging drugs to be used with caution
- BCRP inhibitors to be used with caution

A corresponding list for programming purposes will be saved in a separate document.

However, some patients may take these substances during the treatment period so these concomitant medications will be selected via programming and tabulated and listed in the Clinical Study Report.

3.8 Efficacy evaluation

The efficacy endpoints based on the tumor assessments will be derived according to the RECIST guideline version 1.1 (see Section 2.5 and Appendix 3 of the Clinical Study Protocol for details). The tumor endpoint derivation is based on the sequence of overall lesion responses at each assessment/time point. However, the overall lesion response at a given assessment/time point may be provided from different sources as illustrated in [Table 3-2](#).

Table 3-2 Sources for overall lesion response

Source 1	Investigator (local radiology) reported overall lesion response
Source 2	Novartis-calculated overall lesion response based on raw (i.e. individual lesion) measurements from investigator (local radiology)
Source 3	Final central radiology review committee reported overall lesion response

The primary efficacy analysis will be based on the investigator/local radiology review. The investigator reported overall lesion response at each assessment/time point (Source 1 in [Table 3-2](#)) will be used to derive the efficacy endpoints.

Source 2 will be listed against Source 1 and discrepancies between calculated and assigned responses will be identified for data review purposes.

Data from Source 3 will be used for selected supportive efficacy analyses. For central radiology, the final adjudicated data will be listed. Differences in overall responses between local radiology (Source 1) and central radiology (Source 3) will be listed.

3.8.1 Primary efficacy

The primary objective of the study is to determine whether treatment with alpelisib in combination with fulvestrant prolongs PFS compared to treatment with placebo in combination with fulvestrant in men and postmenopausal women with HR+, HER2-negative advanced breast cancer which progressed on or after AI treatment for patients with PIK3CA mutant status as measured in tissue.

PFS based on local radiology assessment is the primary efficacy variable in this study. PFS is defined as the time from the date of randomization to the date of the first documented disease progression or death due to any cause. If a patient has not progressed or died at the analysis cutoff date, PFS will be censored at the time of the last adequate tumor assessment before the cut-off date. Definitions and further details on PFS can be found in Appendix 3 of the study protocol.

Discontinuation due to disease progression (collected on the 'End of Treatment Disposition' and 'End Post Trt Phase Disposition' eCRF) without supporting objective evidence (as defined in [Section 2.4.2](#)) satisfying progression criteria per RECIST will not be considered disease progression for PFS derivation.

3.8.1.1 Primary analysis

The primary analysis of PFS will be based on the local radiological assessments (Source 1 in [Table 3-2](#)) up until the cut-off date defined in [Section 2.2](#). The analysis will be performed on the FAS and will use the default censoring and event date options from [Table 3-3](#), with the

exception of the rules for new antineoplastic therapy given, i.e. event/censoring rules will be based on options A(1), B(1), C1(1), C2(1), D(1), E(1), and F(1). In particular, PFS will be censored at the last adequate tumor assessment if a patient didn't have an event or the event occurred after two or more missing tumor assessments (see [Section 2.4.5](#)). In the primary analysis in this study PFS will not be censored if a new antineoplastic therapy is started; instead, an ITT approach will be used and this new antineoplastic therapy will be ignored for the purposes of PFS derivation (and tumor assessments will continue), i.e. option F(1) in [Table 3-3](#) will be used. A sensitivity analysis will be performed censoring PFS at the last adequate tumor assessment prior to start of new antineoplastic therapy, i.e. using option F(2). Discontinuation of study treatment (for any reason) will not be considered as a reason for censoring.

Table 3-3 Options for event dates used in PFS

Situation		Options for end-date (progression or censoring) ¹ (1) = default unless specified differently in the protocol or RAP	Outcome
A	No baseline assessment	(1) Date of randomization/start of treatment ³	Censored
B	Progression at or before next scheduled assessment	(1) Date of progression (2) Date of next scheduled assessment ²	Progressed Progressed
C1	Progression or death after exactly one missing assessment	(1) Date of progression (or death) (2) Date of next scheduled assessment ²	Progressed Progressed
C2	Progression or death after two or more missing assessments	(1) Date of last adequate assessment ² (2) Date of next scheduled assessment ² (3) Date of progression (or death)	Censored Progressed Progressed
D	No progression	(1) Date of last adequate assessment	Censored
E	Treatment discontinuation due to 'Disease progression' without documented progression, i.e. clinical progression based on investigator claim	(1) Ignore clinical progression and follow situations above (2) Date of discontinuation (visit date at which clinical progression was determined)	As per above situations Progressed
F	New anticancer therapy given	(1) Ignore the new anticancer therapy and follow situations above (ITT approach) (2) Date of last adequate assessment prior to new anticancer therapy (3) Date of secondary anti-cancer therapy (4) Date of secondary anti-cancer therapy	As per above situations Censored Censored Event
G	Deaths due to reason other than deterioration of 'Study indication'	(1) Date of last adequate assessment	Censored (only TTP and [REDACTED])

¹.=Definitions can be found in Protocol Appendix 3 Section 14.3.25².=After the last adequate tumor assessment. "Date of next scheduled assessment" is defined in Protocol Appendix 3 Section 14.3.25.³.=The rare exception to this is if the patient dies no later than the time of the second scheduled assessment as defined in the protocol in which case this is a PFS event at the date of death

3.8.1.2 Hypothesis and test statistic

The overall Type I error for the trial is one-sided 2.5%. The primary efficacy analysis of PFS based on the population of patients with PIK3CA mutant status will be performed at a one-sided 2.0% level of significance. A secondary efficacy analysis of PFS based on the population of patients with PIK3CA non-mutant status will be performed at a one-sided 0.5% level of significance (see [Section 3.8.2.2](#)). This approach guarantees the protection of the overall type I error at 2.5% (based on a Bonferroni adjustment).

The primary efficacy analysis will be the comparison of PFS between the two treatment arms using a stratified log-rank test at a one-sided 2.0% level of significance for the PIK3CA mutant cohort. The strata information will be based on the data obtained from the IRT system that was utilized for randomization.

Assuming proportional hazards model for PFS for the PIK3CA mutant cohort, the following statistical hypotheses will be tested at the one-sided 2.0% level of significance:

$$H_0: \theta_1 \geq 0 \text{ vs. } H_{a1}: \theta_1 < 0$$

where θ_1 is the log-hazard ratio (alpelisib + fulvestrant treatment arm vs. placebo+fulvestrant treatment arm) of PFS.

3.8.1.3 Kaplan-Meier estimates

The survival distribution of PFS will be estimated using the Kaplan-Meier method. The results will be plotted graphically (Kaplan-Meier curves) by treatment arm. The plots will display the number of patients at risk at equidistant time points. The median, 25th and 75th percentiles for PFS for each treatment arm will be provided with associated 95% confidence intervals. The survival probabilities at 6, 12, 18 months, and the associated 95% confidence intervals will be summarized by treatment arm. Kaplan-Meier estimates will be obtained using PROC LIFETEST with method=KM option in SAS. The loglog option available within PROC LIFETEST will be used to compute the confidence intervals.

The purpose of the two-sided 95% CI is to give an estimate of the respective treatment effect together with a comparable measure of reliability but not for reconstructing the test decisions.

3.8.1.4 Hazard Ratio

The PFS hazard ratio with two-sided 95% confidence interval will be derived from the stratified Cox proportional hazards model for each cohort. In this analysis the baseline hazard function will be allowed to vary across strata. SAS PHREG procedure with ties=EXACT option will be used to carry out this analysis in which the model statement will include treatment arm variable as the only covariate and the STRATA statement will include the stratum information as obtained via IRT.

3.8.1.5 Sensitivity analyses of the primary endpoint

Sensitivity analyses are performed only if the analysis of primary endpoint in the PIK3CA mutant cohort shows statistically significant results. Subgroup analyses to explore the intrinsic consistency of any treatment effect found overall are specified in [Section 3.13.2](#).

Per protocol Population

The PPS will be used to perform sensitivity analysis for the primary efficacy endpoint (i.e. PFS) if the primary endpoint is statistically significant.

Different Censoring Mechanisms

Depending on the statistical significance of the primary efficacy endpoint, the following sensitivity analyses will be performed to address the impact of tumor assessment features and censoring rules on primary analyses. The primary efficacy analyses in each cohort; i.e. the stratified log-rank test, Kaplan-Meier estimates, estimate of the median PFS along with 95% confidence interval, and hazard ratio obtained using the Cox proportional hazards model, will be repeated (as appropriate) based on the data obtained:

1. If more than 10% patients have two or more consecutive missing assessments prior to PFS event, primary PFS analyses will be repeated using investigator/local assessment (Source 1 in [Table 3-2](#)) on the FAS and taking the event whenever it occurs - even after two or more missing tumor assessments. The following options from [Table 3-3](#) will be used: A(1), B(1), C1(1), C2(3), D(1), E(1) and F(1). In the summary table, this approach is referred as 'Actual event PFS analysis'
2. If more than 10% patients have two or more consecutive missing assessments prior to PFS event, primary PFS analyses will be repeated using investigator/local assessment (Source 1 in [Table 3-2](#)) on the FAS and backdating events occurring after missing tumor assessments. The following options from [Table 3-3](#) will be used: A(1), B(1), C1(2), C2(2), D(1), E(1), and F(1). In the summary tables, this approach is referred as 'Backdating PFS analysis' where, the date of next scheduled assessment is defined as the date of the last adequate tumor assessment plus the protocol specified time interval for assessments.
3. Using investigator/local assessment (Source 1 in [Table 3-2](#)) on the FAS and censoring all PFS events that occur after the start of new anti-neoplastic therapy to the time of last adequate tumor assessment done prior to the therapy start date.
4. If there are any COVID-19 related deaths, an additional sensitivity analysis will be performed to address the potential impact of the COVID-19 pandemic, using investigator/local assessment (Source 1 in [Table 3-2](#)) on the FAS and censoring all death events related to COVID-19 at the time of the event.

Unstratified Analysis

As a sensitivity analysis to assess the impact of stratification, the two treatment groups will be compared using the unstratified log-rank test. The HR together with the associated 95% confidence interval obtained using the unstratified Cox regression model will also be presented.

Baseline Demographic and Disease Characteristic factors

If the primary endpoint is statistically significant, a multivariate stratified Cox regression model for PFS will be fitted to evaluate additionally the effect of other baseline demographic or disease characteristics on the estimated hazard ratio. This model will include the following key

prognostic factors: ECOG performance status (0 vs. 1), bone lesions only at baseline (yes or no), number of prior lines of therapy in any setting (1st line vs 2nd line) and region (see [Section 3.13.2](#) for definitions).

All covariates will be included in the model regardless of their observed significance (p-value for given covariate). Forest plots for these factors will be provided, please see [Section 3.13.2](#).

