- Date of last contact is defined as the last date the patient was known to be alive. This corresponds to the latest date for either the visit date, lab sample date or tumor assessment date. If available, the last known date patient alive from the survival follow-up page is used. If no survival follow-up is available, the date of discontinuation is used as last contact date.
- Date of secondary anti-cancer therapy is defined as the start date of any additional (secondary) antineoplastic therapy or surgery.

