2.4.3 Best overall response (BOR)

The evaluation of BOR will be assessed using RECIST 1.1. The definitions and the details on the derivation of BOR are given in Appendix 3 of the study protocol.

The best overall response will usually be determined from response assessments undertaken while on treatment. In addition, only tumor assessments performed before the start of any further anti-neoplastic therapies (i.e. any additional secondary anti-neoplastic therapy with the exception of palliative radiotherapy) will be considered in the assessment of BOR.

Further anti-neoplastic therapies will be identified from the data collected on ‘Antineoplastic therapy since discontinuation of study treatment- Medication’ eCRF and “Antineoplastic Therapy - Radiotherapy” eCRF.

Palliative radiotherapy is the only setting of radiotherapy allowed during a study. It will not be considered as an antineoplastic therapy for the assessment of BOR.

Continuation of fulvestrant monotherapy as 1st new anti-neoplastic therapy after end of treatment without prior PD and collected in the ‘antineoplastic therapy since discontinuation of study treatment- Medication’ eCRF, will not be considered as an anti-neoplastic therapy for the assessment of BOR.

Since the tumor assessments are performed every 8 weeks (+/- 7 days) after randomization during the first 18 months and every 12 weeks (+/- 7 days) thereafter, the standard definition of a best overall response evaluation of “stable disease”, “progressive disease” or “unknown” given in the Appendix 3 of the study protocol requires an adjustment. Best overall response for each patient is determined from the sequence of overall (lesion) responses according to the following rules:

- CR = at least two determinations of CR at least 4 weeks apart before progression
- PR = at least two determinations of PR or better at least 4 weeks apart before progression (and not qualifying for a CR)
- SD = at least one SD assessment (or better) > 7 weeks after randomization date (and not qualifying for CR or PR).
- Non-CR/non-PD = at least one non-CR/non-PD assessment (or better) > 7 weeks after randomization date (and not qualifying for CR or PR). This applies only for patients with non-measurable disease alone at Baseline.
- PD = progression ≤ 17 weeks after randomization date (and not qualifying for CR, PR, SD or non-CR/non-PD).

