Patients receiving any further anti-neoplastic therapy before definitive worsening will be censored at the date of their last assessment before the start date of the therapy. Patients that have not worsened as of the cutoff date will be censored at the date of their last assessment before the cutoff.

Patients without baseline ECOG PS or without any post-baseline ECOG PS will be censored at the date of randomization with censoring reason being ‘No baseline score’ or ‘No post-baseline score’, respectively. However, patients without post-baseline ECOG PS who die within 62 days after date of randomization will be counted as having a definitive deterioration of the ECOG PS at the date of death.

This threshold corresponds to twice the protocol defined ECOG assessment interval plus twice the time window around each assessment: (2 x 28 days)+(2 x 3 days), i.e. 62 days.

Kaplan-Meier estimates will be constructed for each treatment arm in each cohort. The median, 25th and 75th percentiles for time to definitive deterioration for each treatment group will be obtained along with 95% confidence intervals.

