Time to 10% deterioration in the global health status/ [REDACTED] will be assessed in each cohort. 10% deterioration is defined as a worsening in score by at least 10% compared to baseline, with no later improvement above this threshold observed during the treatment period, or death due to any cause. Time to deterioration is the number of days between the date of randomization and the date of the assessment at which deterioration is seen. If a patient has not had an event prior to analysis cut-off, start of new anti-neoplastic therapy, lost to follow-up, or withdrawal of

consent, the time to deterioration will be censored at the date of the last evaluation before the earliest of these dates. If deterioration is observed after two or more missing assessments, time to deterioration will be censored at the date of the last assessment prior to the deterioration. Patients with no baseline data will be censored at Day 1. Death is considered as an event when it occurs within a period of time defined by 2 times the period between two assessments as planned in the study protocol. This avoids overestimating the time to definitive worsening in patients dying after an irregular assessment scheme. Patients who die after more than twice the planned period between two assessments since the last assessment are censored at the date of their last available questionnaire.

Time to 10% deterioration will be compared between the two treatment arms using a stratified log-rank test (strata based on IRT data) and the survival distributions will be presented descriptively using Kaplan-Meier curves. Summary statistics from the Kaplan-Meier distributions will be determined, including the median time to 10% deterioration and the proportions of patients without 10% deterioration at 6, 12, 18 months. Both point estimates and 95% CIs will be presented. A stratified Cox regression model will be used to estimate the hazard ratio (HR) of time to deterioration, along with 95% confidence interval. Sensitivity analysis of time to definitive deterioration with different cut-off definitions (e.g. 5%, 15%) may also be considered if the number of events per arm is judged sufficient to draw relevant conclusions.

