3.9.1.5.1 Time to onset of any CTC grade ≥ 2 [≥ 3] event

Time to onset of CTC grade ≥ 2 [≥ 3] event will be summarized using the Kaplan-Meier method. Median time to onset and 95% CI will be provided. In addition, Ascending Kaplan-Meier plots will be generated.

Time to onset of CTC grade ≥ 2 [≥ 3] event is defined as the time from the start of treatment to the start date of the first incidence of an event of CTC grade ≥ 2 [≥ 3] i.e. time in days is calculated as (start date of first occurrence of the event) – (date of first dose of study treatment) +1.

In the absence of an event during the on-treatment period, the censoring date applied will be the earliest of the following dates:

- end date of on-treatment period (end of study treatment + 30 days).
- death date
- start date of new antineoplastic therapy (with the exception of palliative radiotherapy or fulvestrant monotherapy) before experiencing any CTC grade ≥ 2 [≥ 3] event.
- data cut-off date.
- withdrawal of informed consent date

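### Fulvestrant continued alone after both study drugs end is not new therapy for response or AESI onset, yet it censors patients in the PFS new-therapy sensitivity analysis and in QoL deterioration

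*SAP*

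**What the plan says.** Two SAP analyses exempt this treatment:

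- Section 2.4.3 (best overall response) describes "Continuation of fulvestrant monotherapy as 1st new anti-neoplastic therapy after end of treatment without prior PD", as captured on the eCRF page for treatment after discontinuation, and says it does not count as anti-neoplastic therapy. The exemption is stated for BOR only.
- Section 3.9.1.5.1 (time to AESI onset) censors at new antineoplastic therapy, "with the exception of palliative radiotherapy or fulvestrant monotherapy".

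Four analyses censor at new therapy and carry no such exception:

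- Section 3.8.1.5 item 3 (PFS sensitivity): "censoring all PFS events that occur after the start of new anti-neoplastic therapy to the time of last adequate tumor assessment done prior". The reference point is the day on which the new treatment begins.
- Section 3.8.2.9 (time to 10% QoL deterioration): "If a patient has not had an event prior to analysis cut-off, start of new anti-neoplastic therapy, lost to follow-up, or withdrawal of". Withdrawn consent closes that list, and censoring falls on the most recent evaluation ahead of whichever comes first.
- Section 3.8.2.8 (ECOG deterioration): "Patients receiving any further anti-neoplastic therapy before definitive worsening will be censored at the date of their last assessment" before that therapy.
- Section 3.9.2.1 (laboratory glucose, onset and resolution): the start of new anticancer therapy is one of the listed censoring dates.

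The general definition in Protocol Appendix 3 (14.3.26) does not fill the gap: "Date of secondary anti-cancer therapy is defined as the start date of any additional (secondary) antineoplastic therapy or surgery". The primary PFS analysis ignores new therapy altogether (SAP 3.8.1.1, option F(1)). For palliative radiotherapy, Protocol 14.3.28 already says that treatment given for pain or for lytic lesions at fracture risk is not cancer therapy for BOR and PFS. SAP item 3 does not repeat this.

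**The concern.** Fulvestrant alone is the active part of the control regimen. A patient who ends both study drugs without progression and then goes on with fulvestrant has not moved to a different treatment, and 2.4.3 and 3.9.1.5.1 treat such a patient accordingly. Read literally, item 3 and 3.8.2.9 censor that same patient.

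The discarded data would exist. Protocol 4.1.4 continues tumor assessments after a new antineoplastic treatment starts, and Table 7-10 continues the questionnaires through efficacy follow-up until progression. If patients end treatment for reasons linked to alpelisib and their risk then resembles control, removing the later follow-up takes out the part of the alpelisib arm where the benefit has gone. The censoring would be informative in an analysis that is meant to show robustness to censoring rules. For QoL deterioration the rule governs the main analysis of a named secondary endpoint. Protocol 10.5.4 does not mention censoring at new therapy there; the SAP adds it.

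**Working it through.** **Who is reached.** Protocol 6.1.2 lets a patient who permanently stops one drug continue the other as trial therapy. Section 6.3.1.2 says the same for fulvestrant after a long alpelisib/placebo delay, and 7.1.3 says such a patient is not withdrawn. SAP 2.1.1 makes fulvestrant a study drug, and SAP 2.1.5 dates the end of study treatment by the last dose of either component. So stopping only alpelisib/placebo triggers no censoring. The rule reaches patients who end both drugs and then have fulvestrant entered on the post-discontinuation page. The 2.4.3 wording shows that such entries are expected.

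**Which analyses feel it.**

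- PFS item 3 and QoL: yes, because assessments continue after treatment ends.
- ECOG: scheduled only at cycle visits and end of treatment (Protocol 7.2.2.4), so the last assessment before off-study fulvestrant is normally the same with or without the exception. Only deaths soon after it could change.
- Laboratory glucose: already cut at last dose plus 30 days, so an exception adds at most 30 days.

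**Design inputs (SAP 3.14 and 3.12.1).** HR 0.6, medians 7.0 and 11.67 months, 340 patients 1:1, mutant-cohort accrual of 5, 14 and 24 per month, 243 events. The fixed-design power is Φ(|ln 0.6|·√243/2 − 2.054) = Φ(3.98 − 2.05) = 97.3%. Simulating looks at 97, 185 and 243 events, with futility at Z < 1.489 enforced and efficacy bounds of 3.719 and 2.054, gives 84.0%, against the stated 83.80%. The futility-stop probabilities are 15.2% under HR 0.6 and 93.2% under HR 1 (stated 15.31% and 92.98%). The inputs are read correctly; the point itself changes none of these figures.

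**Illustration for item 3.** The documents give no rates, so these are assumed. Monthly hazards are ln 2/7 = 0.099 for control and 0.6 × 0.099 = 0.059 on alpelisib. The stated share of each arm is assigned to end both drugs at a time uniform on 0.5-6 months and take fulvestrant; those still event-free then are affected. The alpelisib hazard returns to control level after the stop. Scans are every 8 weeks, there is light dropout, no other new therapy, and the cut-off is at 243 events; 1,500 trials, unstratified Cox model.

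| Alpelisib / control affected | HR with exception | HR as written | Difference | Events |
|---|---|---|---|---|
| 2% / 0% | 0.602 | 0.599 | 0.003 | 243 → 241 |
| 5% / 1% | 0.610 | 0.601 | 0.009 | 243 → 237 |
| 10% / 2% | 0.619 | 0.601 | 0.018 | 243 → 231 |
| 20% / 4% | 0.644 | 0.607 | 0.037 | 243 → 219 |

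Two variants:

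- Equal shares, 10% / 10%: 0.625 against 0.602, a difference of 0.023. The shift comes from the assumed change in hazard and does not need an imbalance between arms.
- 10% / 2% with no change in hazard after the stop: 0.598 against 0.603, so the analysis as written is 0.005 higher.

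**Scale.** The standard error of log HR with 243 events is about 2/√243 = 0.128. The 2% row is ln(0.602/0.599)/0.128 = 0.04 standard errors, and the 20% row is ln(0.644/0.607)/0.128 = 0.46.

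**The case against.** The strongest objection is that this touches little. Primary PFS, alpha, power and the testing hierarchy are untouched. Item 3 is run only after a significant primary result and carries no decision rule. Censoring at any recorded new therapy is a legitimate stress test beside the primary approach, and SAP 3.8.1.5 states the aim only as examining tumor-assessment features and censoring rules. The working definition may also sit in the separate programming specifications named in SAP section 1, which are not available here. All of this stands, and it limits the point to a low-cost correction. It does not explain why the same treatment record counts in one analysis and not in another.

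A reader might go further and infer that patients who stop alpelisib for toxicity and stay on fulvestrant are censored in general. The documents do not support that: such patients remain on study treatment unless both drugs end.

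A reader might also infer that the censoring falls mainly in the alpelisib arm. That is plausible, but no document states it. The only earlier figures are drug discontinuation for adverse events of 13% at 400 mg and 0% at 300 mg, the latter in 9 patients (Protocol 1.2.3.3 and Table 1-2). They do not measure off-study fulvestrant use.

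**Conclusion.** The inconsistency is real and can be read directly from the text. It matters for PFS sensitivity item 3 and for time to 10% QoL deterioration; in ECOG deterioration and laboratory glucose it has little practical effect. Its size is unknown, because neither the number of affected patients nor their split by arm is given.

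On the assumed range of 2-20% of the alpelisib arm and 0-4% of control, with the hazard returning to control level, item 3 as written gives an HR 0.003-0.037 lower, which is more favorable to alpelisib, and loses 2-24 of 243 events. Without a change in hazard the difference is about 0.005 and slightly unfavorable. With no such patients it is zero. No size was computed for QoL.

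**What to change.** Define new anti-neoplastic therapy once in the SAP, with the 2.4.3 fulvestrant exception (first anti-cancer treatment after both drugs end, no progression so far). Derive one shared flag and use it in 3.8.1.5 item 3 and 3.8.2.9, and for consistency in 3.8.2.8 and 3.9.2.1. Carry into item 3 the palliative radiotherapy exception that Protocol Appendix 3 already gives for PFS. Report by arm how many patients had such fulvestrant continuation, so that a reader can see whether the rule matters.

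The cost is a few lines of SAP wording, one derived variable and one table row. The Amendment 5 text in the protocol records that the primary endpoint has been met, so a change made now to item 3 should be labeled as such, or the result shown both ways.
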